# **SECTION 1. ABSTRACT**

---

## **Study Hypothesis/Question**

The central hypothesis of the proposed work is that protein-enriched human milk diets during the first 2 weeks after birth increase fat-free mass(FFM)-for-age Z scores and promote maturation of the gut microbiome at term equivalent age in extremely preterm (EPT) infants.

## **Study Design Type**

Parallel-group, masked randomized controlled trial in which study participants fed human milk will be randomly assigned in a 1:1 allocation ratio to receive either a protein-enriched human milk diet (intervention group) or a usual human milk diet (control group) within the first 96 hours after birth..

## **Eligibility Criteria**

EPT infants with gestational age of 28 weeks or less admitted to the neonatal unit at the University of Alabama at Birmingham (UAB) Hospital will be included. Infants with major congenital anomalies and infants with a terminal illness in whom decisions to withhold or limit life support have been made will be excluded.

## **Study Intervention/Methods**

Written informed consent will be obtained within the first 96 hours after birth to allow treatment allocation before or on the first day of enteral feeding via orogastric tube. Infants in the intervention group will receive expressed human milk or donor human milk on feeding day 1 (within the first 96 hours after birth). On feeding day 2, a human milk-based product that increases protein content (Prolact®, Prolacta Bioscience, Inc. City of Industry, CA) will be added to human milk. This practice will continue until standard bovine-based human milk fortifiers are ordered. Infants in the control group will receive expressed human milk or donor human milk from feeding day 1. This practice will continue until standard bovine-based products are ordered.

## **Primary Outcome**

The primary efficacy outcome will be FFM-for-age Z-score at 36 weeks of postmenstrual age (PMA). The primary microbiological outcome will be composition and diversity of the gut microbiome.

## **Secondary Outcome(s)**

Secondary efficacy outcomes will include postnatal growth failure (PGF), FFM, %FFM, body fat (BF), and %BF at 36 weeks PMA, growth velocity rate (g/kg/d) between birth and 36 weeks PMA, and anthropometric measurements at 36 weeks PMA (weight, head circumference, and length). The primary safety outcomes will include intestinal perforation, NEC stage 2 or greater, culture-proven sepsis, and death.

## **SECTION 2. STATEMENT OF PROBLEM**

---

### **2.1. PRIMARY HYPOTHESIS OR QUESTION**

Protein-enriched human milk diets during the first 2 weeks after birth increase FFM-for-age Z scores at term equivalent age in extremely preterm (EPT) infants.

### **2.2. SECONDARY HYPOTHESIS OR QUESTIONS (S) (IF APPLICABLE)**

Protein-enriched human milk diets during the first 2 weeks after birth promote maturation of the gut microbiome at term equivalent age in extremely preterm (EPT) infants.

### **2.3. BACKGROUND AND RATIONALE**

Limited enteral nutrition aggravates the problem of cumulative nutritional deficits during the first 2 weeks after birth and increases the risk of postnatal growth failure in extremely preterm (EPT) infants born at 28 weeks of gestation or less. Postnatal growth failure occurs in approximately 6 of every 10 EPT infants by the time they reach 36 weeks of postmenstrual age (PMA). EPT infants with postnatal growth failure have a higher risk of adverse health outcomes, particularly when they have more fat mass (FM) gains than fat-free mass (FFM) gains. To restore cumulative nutritional deficits and prevent postnatal growth failure in EPT infants with limited enteral nutrition during the first 2 weeks after birth, most clinicians prescribe protein-enriched diets to promote catch-up growth only after full enteral nutrition is established. Emerging clinical evidence suggests that this approach is not effective to improve health outcomes in EPT infants.

Likewise, increasing evidence from translational studies suggest that the practice of limiting enteral nutrition in early postnatal life shapes not only growth and FFM accretion, but also development of the gastrointestinal (GI) tract and composition of the gut microbiome. EPT infants unable to receive sufficient enteral nutrition during the first 2 weeks after birth need innovative early life dietary interventions. Not addressing this problem will perpetuate the practice of limiting enteral nutrition in EPT infants during a critical period of development in which human milk diets could influence development of the GI tract and help define composition of the gut microbiome.

## **SECTION 3. METHODS**

---

### **3.1. STUDY POPULATION**

Extremely preterm infants with gestational ages of 22 0/7 to 26 6/7 weeks of gestation admitted to the UAB hospital. This study population has been selected based on the frequency of feeding problems observed at these lower gestational ages and the increased risk of postnatal growth failure in this vulnerable population.

#### **3.1.1. Inclusion Criteria**

- Gestational age of 22 0/7 to 26 6/7 weeks of gestation
- < 48 hours postnatal age

#### **3.1.2. Exclusion Criteria**

- Major congenital/chromosomal anomalies
- Terminal illness requiring limited or withheld support

### **3.2. DETAILED STUDY PROCEDURES**

#### **3.2.1. Screening**

All 22 0/7 to 26 6/7 weeks of gestation infants admitted to the UAB neonatal unit will be screened to determine eligibility for the trial. To maximize the generalizability of our results, we will screen inborn and outborn infants in their first 96 hours to allow adequate time for informed consent, identify terminally ill infants, and exclude early deaths unrelated to enteral feeding.

#### **3.2.2. Consent Procedures**

Written informed consent will be obtained by the first 96 hours after birth to allow treatment allocation before or on the first day of enteral feeding. If a potential participant is identified, a member of the study will see the parents and/or mother in her room or the baby's room and explain the study. The risks and benefits will be discussed with the parents and time will be given to them to ask questions. It will be made known to them that no treatment will be withheld from their infant if they participate in the study. Randomization will define study group assignment.

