#### **3.2.3. Randomization Procedures**

[figure not shown]
Participants will be randomly assigned to one of the study groups following computer-generated random-block sequences and with the use of numbered, opaque, sealed envelopes, which will be opened in sequential order only after informed consent is obtained. Twin infants will be randomized individually.

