### 3.2.4. Study Intervention and Comparison

Usual feeding practices in our neonatal unit include: 1) administration of enteral feeds as intermittent bolus gavage every 3 hours; 2) initiation of trophic feeds within the first 96 hours after birth with 20-25 ml/kg/d; 3) progression of enteral feeds with daily increments of 20-25 ml/kg/d usually before postnatal day 7; 4) use of donor human milk as an alternative to mother's own milk if the mother is not able to supply her own milk, and 5) addition of bovine-based products that increase protein content of human milk at approximately postnatal day 14 after full enteral nutrition is established ( $> 120$  ml/kg/d) [Figure 4].

Intervention group: Infants in the intervention group will receive expressed human milk or donor human milk on feeding day 1 (within the first 96 hours after birth). On feeding day 2, a human milk-based product that increases protein content (Prolact®, Prolacta Bioscience, Inc. City of Industry, CA) will be added to human milk. This practice will continue until standard bovine-based human milk fortifiers are ordered.

Control group: Infants in the control group will receive expressed human milk or donor human milk from feeding day 1. This practice will continue until standard bovine-based products are ordered.

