### **4.1. STATISTICAL ANALYSIS PLAN**

All statistical analyses will use two-tail alpha to reject null hypotheses at 0.05, using R software. Continuous variables will be summarized as means  $\pm$  standard deviations (SD) or as medians and interquartile ranges (IQRs). Categorical variable will be summarized as frequencies and proportions. Group differences will be evaluated using the T Test or Wilcoxon test for continuous variables and chi-square for categorical variables. The effect size of the primary outcome will be expressed as the mean difference with 95% confidence intervals (CIs). Risk ratios (RRs) with 95% CIs will be reported for categorical outcomes. All of the efficacy and safety outcomes of the trial will be analyzed with the intention-to-treat principle.

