### **4.2. SAMPLE SIZE AND POWER ESTIMATES**

We used our own institutional data from a previous enteral feeding trial to calculate the sample size for this trial. To detect a 0.5-difference in FFM-for-age Z-scores between groups with SD of 1, 0.05 level of significance, and 80% power for a T-test that compares means from

two independent samples, we estimated that a sample size of 126 patients will be necessary in this superiority trial. Anticipating that approximately 20% of study participants will be lost to follow-up for assessment of the primary outcome at 36 weeks PMA, we will add 12 patients to each group and increase the sample size to 150. We will include a total of 75 patients in each group (n=150).

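### Allocation always precedes the first feed that differs between arms, so infants lost in between use up randomised places and dilute the safety risk ratios, without biasing the comparison

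*Combined protocol and SAP*

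**What the plan says.** All references are to the combined protocol and SAP.

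- **Latest point for allocation.** Section 3.2.2 has consent obtained by 96 hours "to allow treatment allocation before or on the first day of enteral feeding". The abstract (Study Intervention/Methods) says the same.
- **Earliest point for allocation.** Section 3.2.3 uses numbered sealed envelopes, "which will be opened in sequential order only after informed consent is obtained". No other trigger is named. Under 3.2.5 the nutrition room staff who dispense the feeds also open the envelopes.
- **Start of the contrast.** Section 3.2.4 gives both arms expressed or donor human milk on feeding day 1. The arms part only afterwards: "On feeding day 2, a human milk-based product that increases protein content" is added to the milk of the intervention group.
- **Aim of the screening window.** Section 3.2.1 screens over the first 96 hours, among other reasons to "identify terminally ill infants, and exclude early deaths unrelated to enteral feeding".
- **Limited support.** Section 3.1.2 makes this an exclusion criterion. No rule covers a decision taken after allocation.
- **Analysis.** Section 4.1 analyses all efficacy and safety outcomes by intention-to-treat, with risk ratios for categorical outcomes. Section 4.2 expects about 20% of infants to lack the primary outcome.

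**The concern.** An assignment that is not used until feeding day 2 does not need to be made earlier. In infants of 22 to 26 weeks the first days carry deaths, perforations and decisions to limit care that have nothing to do with the study diet. Once the envelope is open, such an infant belongs to the trial. It takes one of the 150 places, usually supplies no fat-free mass Z-score, and brings any death, perforation or sepsis episode into the safety comparison.

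Section 3.2.1 shows that the authors wanted to keep early deaths unrelated to feeding out of the trial. The permitted timing meets that aim only in part, because the envelope may be opened before the information has emerged. At stake are precision for the primary outcome and the trial's ability to see harm.

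**Working it through.** **1. Length of the interval.** The shortest case is an envelope opened on feeding day 1, which leaves about one feeding day. For the longest case, section 3.3 gives parents at least 24 hours before consent is sought, so consent falls at about 24 hours at the earliest if the approach is made at birth. Feeding day 1 may begin as late as 96 hours, and feeding day 2 about a day later, at about 120 hours. The interval can then reach about 120 − 24 = 96 hours, or four days. The wording allows anything between these two.

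**2. The plan's own sample size.** Inputs: "All statistical analyses will use two-tail alpha to reject null hypotheses at 0.05" (4.1) and "To detect a 0.5-difference in FFM-for-age Z-scores between groups with SD of 1, 0.05 level of significance, and 80% power" (4.2).

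n per arm = 2 × (1.960 + 0.842)² × 1² / 0.5² = 62.8, rounded up to 63, so 126 in total. This reproduces the plan: "we estimated that a sample size of 126 patients will be necessary in this superiority trial".

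**3. Evaluable infants as planned.** Section 4.2 continues: "Anticipating that approximately 20% of study participants will be lost to follow-up for assessment of the primary outcome at 36 weeks PMA". With 150 randomised, 150 × 0.80 = 120 remain, or 60 per arm. Power by normal approximation is Φ(0.5 × √(60/2) − 1.96) = 78.2%.

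**4. Effect of later allocation.** Assumption: a share p of the 150 is lost before the contrast, and this loss lies inside the 20%. The documents give no value for p. Among infants who reach feeding day 2, the later loss is (0.20 − p)/(1 − p), so the share with an outcome is 0.80/(1 − p). Randomising 150 such infants gives 120/(1 − p) evaluable. The consents needed are 150/(1 − p).

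| Assumed p | Infants of 150 | Evaluable | Power | Consents needed |
|---|---|---|---|---|
| 0% | 0 | 120 | 78.2% | 150 |
| 2% | 3 | 122 | 79.0% | about 153 |
| 5% | 7 to 8 | 126 | 80.2% | about 158 |
| 8% | 12 | 130 | 81.5% | about 163 |

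The yield per consented infant stays at 80%. The gain arises because infants who never reach the contrast no longer count towards the 150.

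**5. Safety risk ratios.** Let s be the share of control-arm events that occur before the contrast, where the true ratio is 1. Let R be the ratio afterwards. The expected overall ratio is s + (1 − s) × R. With assumed s = 20% and R = 1.5, it is 0.2 + 0.8 × 1.5 = 1.40.

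For death, assume 20% control mortality and R = 1.5. If 2%, 5% or 8% of infants in each arm die before the contrast, then:
- 2%: (0.02 + 0.18 × 1.5)/0.20 = 1.45
- 5%: (0.05 + 0.15 × 1.5)/0.20 = 1.38
- 8%: (0.08 + 0.12 × 1.5)/0.20 = 1.30

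**The case against.** **Allocation is not fixed at consent.** A reader might infer that infants are randomised at the moment of consent. The text does not say so. Consent is the earliest point, feeding day 1 is the latest, and having the envelopes opened by the staff who dispense the feeds fits opening at feed preparation. The gap may be only one feeding day in practice. A figure in 3.2.3 and Figure 4 cited in 3.2.4 are not available and may show the timing. This stands: several days is what the wording allows, not what it requires. The gap is nevertheless never zero.

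**There are safeguards.** The 96-hour screening window, the exclusion for limited support and the 24 hours for reflection all reduce early losses. They do not close the gap, because none of them acts after the envelope is open.

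**No bias is shown.** A reader might infer that the comparison is distorted or that the fat-free mass difference is diluted. Neither follows. Events before the contrast cannot depend on diet, the groups remain randomised, and caregivers are masked. Infants who die have no Z-score, so they reduce the number analysed and leave the mean difference undiluted. The 20% allowance may already include them.

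**The size is small and assumed.** With 20% control mortality and 75 per arm, a risk ratio of 1.5 has a 95% confidence interval of about 0.85 to 2.65, so a shift to 1.40 is minor beside the sampling error. This stands.

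**The target population changes.** Section 3.2.6 calls the trial pragmatic and 3.2.1 aims for generalisability. Later allocation restricts the conclusion to infants who reach feeding day 2. That is a real choice, although it agrees with the stated aim of excluding early deaths unrelated to feeding.

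**Conclusion.** The point holds as an inexpensive improvement to the design. It is not a flaw in validity. Allocation precedes the diet contrast at every time the protocol permits, and infants lost in between count under intention-to-treat without any possible effect of diet.

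The cost is in precision and in dilution of the safety ratios. Across assumed losses of 2% to 8%, all inside the expected 20%, later allocation moves the evaluable number from 120 to between about 122 and 130. At an assumed 5% it restores the 126 that the plan requires. The safety illustrations, 1.5 falling to between 1.45 and 1.30, rest on assumed event shares, an assumed control mortality and an assumed true ratio. The documents supply none of these, so the direction of the effect is firm and its size is not.

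**What to change.** Separate consent from allocation in 3.2.2, 3.2.3 and 3.2.4, and in the matching abstract text (Study Design Type and Study Intervention/Methods):

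1. Obtain consent as now.
2. Have the study team confirm that the infant is alive, is being fed and still meets no exclusion criterion in 3.1.2. This should not fall to the nutrition room staff, who are not involved in patient care.
3. Have the nutrition room staff then open the next envelope when they prepare the first feed of feeding day 2.
4. Count the 150 from that point. List consented infants who do not reach it as consented, not randomised.
5. Word the age limits so that they govern consent and enrolment and not the opening of the envelope. Feeding day 2 may fall after 96 hours, and the abstract now ties assignment to the first 96 hours. The under-48-hour criterion in 3.1.1 must also be reconciled with the 96 hours in the abstract, 3.2.1 and 3.2.2.

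Milk is identical on feeding day 1, so the selection happens before randomisation and leaves masking and intention-to-treat intact.

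The cost is a wording change, one status check per infant and a few more consents: about 3 to 13 over the assumed range. The plan's own figures (150 available a year, 60% consent, 2.5 years) give 150 × 0.60 × 2.5 = 225 consents, so these fit. The conclusion would apply to infants who reach feeding day 2, and the protocol should say so.

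If the sponsor keeps the present timing, a prespecified supplementary analysis of infants alive and still fully supported at feeding day 2, with intention-to-treat kept as primary, would clarify the safety ratios. It would not recover the places.

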#### **3.2.3. Randomization Procedures**

[figure not shown]
Participants will be randomly assigned to one of the study groups following computer-generated random-block sequences and with the use of numbered, opaque, sealed envelopes, which will be opened in sequential order only after informed consent is obtained. Twin infants will be randomized individually.

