### **Risk to Human Subjects**

Human Subjects' Involvement, Characteristics, and Design. In this clinical trial, 150 study participants will be randomly assigned in a 1:1 allocation ratio to receive either a protein-enriched human milk diet (intervention group) or a usual human milk diet (control group) during the first 2 weeks after birth. Patients admitted to the UAB Neonatal Intensive Care Unit between July 2020 and December 2022 will be screened to determine eligibility for the trial. Our study population will reflect the epidemiology of prematurity in the state of Alabama, with approximately 51% being Black (African-American), 47% White (Non-Hispanic Caucasian), and the remaining 2% Hispanic/Other. This study population has been selected based on the frequency of postnatal growth problems observed in extremely preterm infants and the increased risk of adverse health outcomes in this vulnerable population.

Study Procedures, Materials, and Potential Risks. For study participants, data will be collected from electronic medical records. Data containing identifying information will be available only to the PI and research personnel directly involved with this study. Information about the study

will be shared without individual identifiers. Data will be collected from medical records in accordance with the study protocol. This will include demographic data and other nutrition/feeding data. This protocol will be reviewed by the Institutional Review Board of the University of Alabama at Birmingham.

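### Allocation is not stratified by gestational age, and the plan offers no gestational-age-adjusted comparison that rests on baseline covariates alone

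*Combined protocol and SAP*

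**What the plan says.** On allocation, section 3.2.3 states "Participants will be randomly assigned to one of the study groups following computer-generated random-block sequences", delivered in numbered sealed envelopes opened in order. No stratification factor is named there or in section 3.2.5, which describes the nutrition room opening the envelopes.

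On the population, section 3.1.1 requires "Gestational age of 22 0/7 to 26 6/7 weeks of gestation". Section 3.1 explains the choice by the "frequency of feeding problems observed at these lower gestational ages and the increased risk of postnatal growth failure". The plan thus treats gestational age as prognostic for feeding and growth.

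On outcomes, the abstract says "The primary safety outcomes will include intestinal perforation, NEC stage 2 or greater, culture-proven sepsis, and death". Section 3.2.8 adds respiratory support and BPD at 36 weeks.

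On analysis, section 4.1 names chi-square for categorical variables and says "Risk ratios (RRs) with 95% CIs will be reported for categorical outcomes". Its last paragraph plans adjusted analyses of clinical and microbiome outcomes with seven covariates: feed volume, proportion of human milk, antibiotic days after birth, race, sex, gestational age and maternal antibiotics. It names no model for adjusted binary outcomes and does not say whether the unadjusted or the adjusted result is the main one.

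**The concern.** With 75 infants per arm and no strata, chance can place more of the youngest infants in one arm. If risk differs by gestational age, such an excess moves several safety and respiratory outcomes in the same direction. It may also change who remains for the fat-free mass measurement, for which section 4.2 already expects about 20% loss.

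The natural remedy is an estimate adjusted for gestational age, and the one that is planned does not isolate it. Section 3.2.2 places allocation before or on the first day of enteral feeding, so feed volume and share of human milk are measured after allocation. Antibiotic days can also accumulate after it. The diet, or its complications, could alter all three. Adjusting for them along with gestational age can remove part of a real diet effect or distort it. If the arms differ on gestational age and the crude and adjusted results disagree, the reader has no clean third estimate, and no rule fixed in advance for choosing between the two.

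**Working it through.** **The plan's own figure.** Section 4.2 gives a difference of 0.5, SD 1, two-sided 5% and 80% power. Per arm, n = 2 × (1.96 + 0.84)² / 0.5² ≈ 63, or 126 in total, as stated; this is raised to 150 (75 per arm). The documents give no figure for gestational-age balance, stratum shares or event risks. Those used below are assumptions.

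**1. Chance imbalance.** Let q be the share of infants in a lower stratum. With 75:75 allocation that ignores the stratum (and ignoring the block structure), the number of lower-stratum infants in one arm is hypergeometric. The SD of the between-arm difference in share is 2 × √(q(1−q)/149).

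| q | SD (points) | chance of ≥10 points | chance of ≥15 points |
|---|---|---|---|
| 20% | 6.6 | 15% | 2% |
| 30% | 7.5 | 15% | 3% |
| 40% | 8.0 | 24% | 7% |
| 50% | 8.2 | 19% | 5% |

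The probabilities do not rise smoothly because the counts are whole infants. A simulation of 10,000 allocations in blocks of 4 and 6, with q at 40-50%, gives an SD of 8.0 to 8.2 points and a 21-22% chance of more than 10 points.

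**2. What an imbalance does to one result.** Shift = imbalance × risk gap between strata. With death risks of 35% and 10%, a 10-point imbalance gives 0.10 × 25 = 2.5 points. At q = 40% the overall risk is 0.4 × 35% + 0.6 × 10% = 20%, and the standard error of the difference is √(2 × 0.20 × 0.80/75) = 6.5 points. The shift is therefore a little under 0.4 standard errors.

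**3. Precision from using the stratum in the analysis.** With the same risks in both arms, the fraction of the variance of the risk difference removed is q(1−q) × gap² / [p(1−p)], where p is the overall risk.

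| q | risks, lower / upper | p | fraction removed |
|---|---|---|---|
| 40% | 35% / 10% | 20% | 0.0150/0.1600 = 9.4% |
| 50% | 35% / 10% | 22.5% | 0.0156/0.1744 = 9.0% |
| 40% | 30% / 10% | 18% | 0.0096/0.1476 = 6.5% |
| 40% | 15% / 5% | 9% | 0.0024/0.0819 = 2.9% |

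Nine per cent of 150 is about 14 infants.

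**4. Precision from the second envelope series itself.** Once the analysis adjusts for the stratum, a chance imbalance d costs about (d²/4) × (1/q + 1/(1−q)) of the information. With d² averaging 0.08² = 0.0064 and q = 40%, that is 0.0016 × 4.17 = 0.7%, or about one infant in 150.

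**5. Validity of the unadjusted test.** In 200,000 simulated trials (q = 40%, risks 30% and 10%), the chi-square rejected a true null in 5.2% of trials without strata and in 4.3% with forced stratum balance. With risks of 40% and 10%, the figures were 5.1% and 3.6%. At risks of 30% and 10%, power for a risk ratio of 0.5 was 0.37 without strata and 0.36 with them. Stratifying while keeping the plain chi-square therefore makes the test conservative and gains no power.

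**6. Load on the planned adjusted model.** At an assumed 20% mortality there are 30 deaths, and 30/7 is about 4 events per listed covariate. A rarer outcome leaves fewer.

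**The case against.** The strongest reply is that section 4.1 already adjusts clinical outcomes for gestational age, so the plan leaves it to chance in allocation but not in analysis. That stands, and a reader who inferred that the safety outcomes get only a crude chi-square would be wrong. The reply does not close the point, because the adjustment is bundled with variables that arise after allocation, has no named binary model, and has no stated rank against the crude result.

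A second reply is that unstratified blocked allocation is a valid design for a single-centre trial of 150. That also stands. It would be tempting to say that the safety comparisons are biased or their error rate inflated. They are not: chance imbalance is already covered by the test and its confidence interval, and the error rate stays near 5%. The second envelope series alone buys about one infant of precision.

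Three further inferences go beyond the text:
- Gestational age is nowhere called the strongest risk factor. Section 3.1 ties it to feeding problems and growth failure, not to death, NEC or perforation.
- A single allocation list is the natural reading, but it is inferred from silence, and a figure in section 3.2.3 is not shown.
- The DSMB would not depend on a crude test. Section 4.5.2 has it review all serious adverse events for their relation to the trial.

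**Conclusion.** The point holds as a low-priority improvement. No gestational-age stratification is stated. The stated tests for categorical outcomes are unadjusted, and the only planned gestational-age adjustment includes covariates that the diet could affect. The cost is lost precision and a harder reading of a single result, not invalid inference.

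The loss is about 9% of the variance for death if 40-50% of infants are 22-24 weeks and the risks are 35% and 10%. It falls to about 3% if the risks are 15% and 5%. The chance of a 10-point or larger imbalance is about 15-24% for stratum shares of 20-50%. All shares and risks are assumptions, since the documents give none.

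**What to change.** **Section 3.2.3.** Prepare two envelope series, 22 0/7 to 24 6/7 and 25 0/7 to 26 6/7 weeks, each with random blocks and 1:1 allocation. These cut-offs follow section 3.1.1. The abstract gives 28 weeks or less, so the two ranges must be reconciled before the strata are fixed.

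**Section 4.1.** Make the main comparison stratum-adjusted: Mantel-Haenszel risk ratios for binary outcomes, and gestational age or the stratum as a term in the fat-free mass model. Use baseline covariates only. Any analysis that adds feed volume, share of human milk or antibiotic days should be labelled as exploratory.

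Make the two changes together, since strata with a plain chi-square only make the test conservative. If enrolment has started, the analysis change can still be made before unblinding, and it carries most of the gain.

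**Cost.** A second envelope series, one extra check at allocation, a short edit to each of the two sections, and a possible small difference in arm sizes from incomplete final blocks. With blocks of at most 6 (assumed, as no size is stated), each series can end at most 3 infants apart.
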